3.0 Study Endpoints/Events/Outcomes

3.1 Primary Endpoint/Event/Outcome:

In this study, we will compress and test a variety of formats, sequences, and doses of ADAPT. We will provide two 'first line' ADAPT programs and two slightly more intensive booster ADAPT programs for families who do not 'respond' to the first line intervention. Adaptive intervention strategies involve decision rules that specify how the type or intensity of an intervention should change depending on participants' response on a predetermined indicator of initial progress within an intervention.^{56, 57, 58} Within a SMART, a measure of initial response is used following delivery of an intervention in order to evaluate each families' need for further intervention programming. In this way, programming is tailored to meet the needs of individual families by providing additional services only to those families who are likely to benefit. This measure of initial response is referred to as a primary tailoring variable. In the proposed study, the primary tailoring variable is parental locus of control, a key variable shown in our prior studies to predict change in observed parenting effectiveness, as well as change in other outcomes (PTSD symptoms, suicidality, and child adjustment).

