All measures are listed in the table below and include: (1) The Parenting Locus of Control (PLOC); (2) The Family Interaction Task (FIT); (3) The Alabama Parenting Questionnaire (APQ-22); (4) Deviant Peer Association (PERS); (5) The Behavior Assessment System for Children, Third Edition (BASC-3); (6) Coping with Children's Negative Emotions (CCNES); (7) The UCLA PTSD-Reaction Index (PTSD-RI); (8) the Children's Depression Inventory (CDI); (9) Describing Friends; (10) PTSD Checklist (PCL); (9) Difficulties in Emotion Regulation Scale (DERS); (11) The Five Facet Mindfulness Questionnaire (FFMQ); (12) Receipt of Help (PSI); (13) Alcohol Use Disorders Identification Test (AUDIT); (14) Center for Epidemiologic Studies Depression Scale (CESD); (15) Deployment Risk and Resilience Inventory (DRRI); (16) Differential Ability Scales (DAS-7); (17) Moral Injury (MIES); (18) Parenting Mindfulness (IEM-P); Parenting Identity; (19) NIH Toolbox Flanker (EF – Inhibitory Control); (20) NIH Toolbox Peabody Picture Vocabulary Test; (21) Deviant Peer Association (TPRISK) Process measures include: satisfaction questionnaires, attendance, practice, online use, and coder ratings to measure fidelity.

(i) The PLOC will be used as the primary tailoring variable measure by all participants at 4 weeks following the start of the intervention (when condensed group or online programming is completed). The PLOC is a 22-item questionnaire that takes about 5 minutes. A link sent to each parent's email address will provide access to the questionnaire. The results of this questionnaire will determine responder status for each individual. If a parent scores below the cut-score

threshold on the PLOC or does not complete the PLOC, that family will be re-randomized to the second stage ADAPT interventions.

(ii) Context measures:

- (a) Demographic information such as gender, age, racial, and ethnic identity for parent and child;
- (b) employment;
- (c) income,
- (d) date/s and number of deployments for parents. Number and length of deployments will be assessed from 3 open-ended questions to obtain information about the extent of respondents' deployment history. Combat exposure will be measured using subscales from the DRRI, an ecologically valid instrument for assessing risk and resilience factors among military personnel participating in recent and current deployments.

(iii) Parenting practice measures:

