17.0 Data Management

17.1 Data Analysis Plan:

Analyses will be conducted in several steps, starting with preliminary and preparatory analyses including data reduction and evaluation of psychometric properties, followed by evaluation of missing data of criterion measures. For the primary efficacy evaluation aims of main effect components and the four adaptive intervention strategies we will employ standard normal theory Analysis of Covariance factorial and fractional factorial analyses to address study aims using pre-post assessment scores for parent and child adjustment constructs. To address the non-independence of subjects in the embedded adaptive intervention designs we will estimate Linear mixed models and weighted least squares regressions for estimation of the embedded adaptive intervention contrasts. Descriptive statistics (mean, range, SD) will be used in reporting participation, satisfaction (for fathers and mothers), and implementation fidelity (for each provider and the group of ADAPT providers).

17.2 Power Analysis:

First, we chose a power convention of .80 with a two-sided alpha level of .05 to reduce the probability of obtaining a false positive improvement or intervention effect rejecting the null when it is true (Type-I error at 5% chance). Second, we powered the study to detect small to medium effect sizes for the first and second stage randomizations. The first stage randomization is allocated with a 1:1 ratio to group conditions as depicted in Figure 6. Based on the ROC analyses we estimate a potential 50% non-response rate for both the online and weekend condensed groups. After the Week 4 assessment of response criteria, non-responders will also be randomized to second stage interventions with a 1:1 allocation.

More specifically, power needed to be estimated by addressing the restricted randomization scheme and appropriate weighting of the overrepresentation of responders and underrepresentation of nonresponders. We employed procedures outlined by Oetting and colleagues for estimating power in SMART trial designs. As recommended, we specified an alpha level of .10 and power of .80. The first main research question (2a) addresses main effects of initial stage randomization,

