the second question (2b) addresses the main effects of the second stage randomization for non-responders. Finally, the third main question (2c) addresses the overall optimal adaptive intervention strategy for military. Following methods outlined by Oetting et al. (2011), the proposed SMART trial is adequately powered to detect small to medium effects for Research Questions 2a, 2b, and 2c. Based on our prior studies outlined above, power was estimated using an estimated 10% to 20% attrition over the study. See chart below.

ADAPT SMART Trial Minimally Detectable Effect (MDE) with .80 Power and 10% and 20% Attrition					
Total Sample	Research Question	Analysis Contrasts	Correct Strategy p	10%	20%
				Attrit. MDE δ	Attrit. MDE δ
525-10% = 473	Q2a	[A+B+C] vs. [D+E+F]		.324	.343
262-10% = 236	Q2b	[B+E] vs [C+F]		.458	.485
Nmax = 473 ¹	Q2c	[A+B]vs [A+C]vs [D+E]vs [D+F]	.95	.285	.301

17.3 Data Integrity:

Site coordinators and the project manager will oversee assessment technicians and conduct quality control checks regularly throughout the data collection process. If needed, additional training will be provided to assessment technicians. Video recordings of family interaction tasks will be monitored by the coding coordinator to ensure high quality and consistency across assessment technicians. Survey data will be cross-checked and cleaned shortly after in-home assessments are conducted to ensure data were collected accurately as well as resolve any discrepancies in key study variables (e.g., deployment status, marital status, gender, etc).

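### For the booster contrast (Q2b), the plan states no use for the week-4 PLOC beyond the responder cut; naming it as a covariate would buy a modest, nearly free gain in precision

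*Combined protocol and SAP*

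**What the plan says.** Section 17.1 plans factorial analysis of covariance "using pre-post assessment scores for parent and child adjustment constructs", with mixed models and weighted regressions for the embedded strategies. It gives no full covariate list. The only adjustment variable named elsewhere is relationship status, in section 9.1.

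Section 17.2 states that "the second question (2b) addresses the main effects of the second stage randomization for non-responders". Non-responders are allocated 1:1, and no stratification factor is named.

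Under sections 5.2 and 5.3, T1 precedes the intervention, the PLOC is completed 4 weeks after the program starts, and the next scheduled assessment is T2, at 6 months from baseline. Section 5.2 uses the week-4 PLOC to set responder status: if a parent scores below the cut "or does not complete the PLOC, that family will be re-randomized to the second stage ADAPT interventions". Section 3.1 calls parental locus of control "a key variable shown in our prior studies to predict change in observed parenting effectiveness" and says that it also predicts change in other outcomes. No correlation is given.

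**The concern.** For Q2b the relevant baseline is the moment of the second randomization. The T1 score predates the first-stage program, so it cannot show where a family stood when the booster was assigned. The week-4 PLOC can, at least in part, and by the protocol's own account its construct carries information about outcome.

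The re-randomized group is mixed. It holds families just below the cut, families well below it, and families with no form at all. Outcome variation linked to these differences stays in the error term unless the model includes them, and Q2b already has the largest minimally detectable effect (MDE) in the section 17.2 table: .458 at 10% attrition and .485 at 20%.

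Silence has a second cost. If the covariate is not named in advance, using it later becomes a choice made after outcomes have been seen.

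**Working it through.** **1. The plan's own figure.** Inputs from section 17.2: N = 236 (262 less 10%), 1:1 allocation, power .80, and two statements of alpha. One reads "we chose a power convention of .80 with a two-sided alpha level of .05"; the other reads "As recommended, we specified an alpha level of .10 and power of .80". For two equal groups with SD 1, MDE = (z for alpha + z for power) × √(4/N).

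- N = 236, alpha .05 two-sided: (1.960 + 0.842) × √(4/236) = .365.
- N = 236, alpha .10 two-sided: (1.645 + 0.842) × √(4/236) = .324.
- N = 118, alpha .10 two-sided: 2.487 × √(4/118) = .458, the printed value.
- N = 105 (half of 210, the 20% attrition number), alpha .10 two-sided: 2.487 × √(4/105) = .485, also the printed value.

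The printed Q2b values therefore match half the stated sample at alpha .10. The Q2a row behaves the same way: 236.5, half of 473, gives .323 against the printed .324. Any gain from a covariate should be expressed as a proportion, which does not depend on how this is resolved.

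**2. Validity of the covariate.** The order is T1, first randomization, first-stage program, week-4 PLOC, second randomization, booster. Both the score and its missingness are settled before booster assignment, so adjusting for them cannot bias the booster contrast. For Q2a the same score is measured after randomization and may be affected by the first-stage program.

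**3. Size of the gain.** These inputs are assumed, because the documents do not give them:

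- r, the full-range correlation between week-4 PLOC and the T1-adjusted outcome: .2 to .5.
- A normally distributed PLOC with the cut at the median. This follows section 17.2, where "we estimate a potential 50% non-response rate for both the online and weekend condensed groups".
- m, the share of re-randomized families without a PLOC: 0 or 20%.

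Only the lower half is re-randomized, so PLOC variance shrinks by the factor k = 1 − 2/π = .363. Among those families R² = r²k / (r²k + 1 − r²). The MDE is multiplied by √(1 − R²(1 − m)).

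| r | R² (m = 0) | MDE factor | MDE drop, m = 0 | MDE drop, m = 20% |
|---|---|---|---|---|
| .2 | .015 | .993 | 0.7% | 0.6% |
| .3 | .035 | .983 | 1.7% | 1.4% |
| .4 | .065 | .967 | 3.3% | 2.6% |
| .5 | .108 | .944 | 5.6% | 4.4% |

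Example for r = .5: .25 × .363 = .0908; .0908 / (.0908 + .75) = .108; √.892 = .944. In sample-size terms, 1/(1 − R²) − 1 runs from 1.5% to 12% more families. Ignoring the truncation would give R² = r², or .04 to .25, which overstates the gain. The table does not count any variance explained by the missing-PLOC indicator itself.

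**The case against.** The case against is that this is a small refinement resting on assumed correlations. Much of that stands.

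- **The gain may be negligible.** The outcomes include coded observation and teacher ratings at 12 and 24 months. PLOC is also part of the wider parent battery, so only information beyond T1 counts. At r = .1, R² is .01 × .363 / (.01 × .363 + .99) = .004. Section 3.1 supports PLOC as a tailoring variable but does not show useful prediction among families already selected below a cut.
- **A reader might infer that the score is thrown away.** The documents do not say so. Section 17.1 is brief and not exhaustive, as the separate mention of relationship status in section 9.1 shows. What can be said is that no further use is specified.
- **A reader might infer that nothing else is recorded between the randomizations.** Section 5.2 lists attendance, home practice, online use and satisfaction data, together with end-of-day workshop evaluations and weekly contact records. Some of these may describe families without a PLOC better than a missing flag would.
- **A reader might infer that first-stage program is left unadjusted.** Section 17.1 plans factorial models and Q2b pools over both first-stage programs, so that factor may already be present. The plan does not say so for Q2b, and confirmation is enough.
- **A reader might infer harm from chance imbalance between boosters.** Under simple 1:1 randomization of 236 families, the PLOC difference has SD 2/√236 = .13 SD units, and a gap above .2 has a probability of about 12%. The standard error already reflects this, and no bias follows.

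These points limit the size and tone of the recommendation. They do not remove the reason for it: the score is already collected, it is a legitimate covariate, and the plan is silent on it.

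**Conclusion.** The point holds as a modest efficiency recommendation. Section 17.1 names only pre-post scores, with the pre score taken before the first-stage program, and gives the week-4 PLOC no stated role in the Q2b model. Adding it would lower residual variance by about 1.5% to 11% and the MDE by about 1% to 6%, on the assumed correlations of .2 to .5, normality and a median cut. The gain shrinks as more re-randomized families lack a form, and is close to nothing if the true correlation is below .2. The validity of the booster comparison is not in question. The mismatch between .458 and N = 236, and the two alpha levels, are larger matters in the same table and need their own correction.

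**What to change.** In section 17.1, prespecify for the Q2b model only, alongside the T1 score:

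1. The week-4 PLOC as one stated family value, for example the lower parent score. The rule should also cover families in which one parent completed the form and the other did not.
2. A missing-PLOC indicator, with a constant filled in for the missing score and a fixed date after which a form counts as missing.
3. First-stage assignment as a factor, or a sentence confirming that the factorial model already includes it.

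State that the week-4 PLOC is not a covariate for Q2a, where it is a post-randomization measurement.

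The cost is a short addition to the text, about two degrees of freedom for the score and the indicator, and the family-score rule. No new data are needed, and families already re-randomized benefit as well. Stratifying the remaining second-stage allocation by PLOC status (below cut or missing) is optional: it would help only families still to be re-randomized and largely duplicates the adjustment.

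### Section 17.2 gives two unreconciled significance levels, two-sided .05 and then .10, so the 5% error rate, 80% power and printed detectable effects for Q2a and Q2b are not shown to belong together

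*Combined protocol and SAP*

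**What the plan says.** Section 17.2 (Power Analysis) opens with: "First, we chose a power convention of .80 with a two-sided alpha level of .05". It explains this level as a "Type-I error at 5% chance" and applies it to powering the first-stage and second-stage randomizations for small to medium effects. Both randomizations are 1:1.

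The second paragraph says that "power needed to be estimated by addressing the restricted randomization scheme and appropriate weighting of the overrepresentation of responders and underrepresentation of nonresponders". It names a published SMART power procedure and continues: "As recommended, we specified an alpha level of .10 and power of .80". It gives no sidedness and does not call .10 a planning value. It then goes straight to questions 2a (first-stage main effect), 2b (second-stage main effect in non-responders) and 2c (best adaptive strategy), and concludes that "the proposed SMART trial is adequately powered to detect small to medium effects for Research Questions 2a, 2b, and 2c".

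The table headed "ADAPT SMART Trial Minimally Detectable Effect (MDE) with .80 Power and 10% and 20% Attrition" gives, at 10% / 20% attrition, .324 / .343 for Q2a, .458 / .485 for Q2b and .285 / .301 for Q2c. The Q2c row also carries a correct-strategy probability of .95. No alpha is printed. Section 17.1 (Data Analysis Plan) sets no test level.

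**The concern.** The two sentences address the same comparisons. The first attaches .05 to the first-stage and second-stage randomizations, which are Q2a and Q2b. The second attaches .10 to the calculation for those questions. No text assigns one level to planning and the other to testing.

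Two things are at stake. First, these are the only statements of alpha in the plan, so a Q2a or Q2b result with two-sided p between .05 and .10 is positive under one and negative under the other. That choice would be left until the data are seen. Second, the claim of 80% power for small to medium effects cannot be checked without knowing the alpha and the variance assumption behind the table.

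**Working it through.** **Inputs.** Power .80 (z = 0.8416) and 1:1 allocation come from 17.2. Analysed N at 10% attrition is printed in the table: 473 for Q2a and 236 for Q2b. At 20% attrition N is derived, not printed: 525 × .8 = 420 and 262 × .8 = 209.6, taken as 210.

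**Formula.** For two groups on a standardized scale, MDE = (z_α + 0.8416) × √(f/N). The plain 1:1 comparison has f = 4.

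**Step 1: plain formula (f = 4).** At 10% attrition, two-sided .05 gives .258 for Q2a and .365 for Q2b. Two-sided .10 gives .229 and .324. Neither level reproduces the printed .324 and .458, so some inflation is built into the table.

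**Step 2: factor implied by each cell**, f = N × [MDE / (z_α + 0.8416)]², and the fit with f = 8 at the .10 quantile:

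| Cell | N | Printed MDE | Implied f, two-sided .10 | Implied f, two-sided .05 | (1.645 + 0.842) × √(8/N) |
|---|---|---|---|---|---|
| Q2a, 10% | 473 | .324 | 8.03 | 6.33 | .3234 |
| Q2a, 20% | 420 | .343 | 7.99 | 6.30 | .3432 |
| Q2b, 10% | 236 | .458 | 8.01 | 6.31 | .4578 |
| Q2b, 20% | 210 | .485 | 7.99 | 6.29 | .4853 |

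At the .10 quantile the factor is 8, exactly twice the plain value. At two-sided .05 it is about 6.3, and at one-sided .10 about 11.0. The implied factor is nearly constant across cells at any alpha, so the cells alone do not identify alpha. The preference for .10 rests on 8 being a simple multiple of 4. The quantile 1.645 also belongs to one-sided .05, and the cells cannot separate the two.

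**Step 3: power at the printed MDEs under two-sided .05**, Φ(MDE × √(N/f) − 1.960):

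- f = 8: .702, .700, .701, .700
- f = 6.3: about .80, by construction
- f = 4: .941, .940, .940, .940

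**Step 4: MDEs at two-sided .05 and 80% power.** Changing alpha alone multiplies each MDE by 2.8016 / 2.4865 = 1.127.

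| | Q2a, 10% / 20% | Q2b, 10% / 20% |
|---|---|---|
| Printed | .324 / .343 | .458 / .485 |
| Two-sided .05, f = 8 | .364 / .387 | .516 / .547 |
| Two-sided .05, f = 4 | .258 / .273 | .365 / .387 |

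Q2c was not reproduced. Its criterion is a selection probability, and nothing here extends to it.

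**The case against.** The strongest reply is that .10 is only an input to the cited SMART procedure and .05 is the test level. The second paragraph is about estimating power, so this reading is plausible. But the plan does not say it, and if it is right, the 80% in the table is not shown to hold at the test level.

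A second reply is that 17.1 plans analysis of covariance on pre-post scores, while the figures above are unadjusted. If the printed MDEs are in raw standard-deviation units, adjustment multiplies the factor by 1 − r². An assumed baseline correlation of r = .46 turns 8 into 8 × (1 − .2116) = 6.3 and restores 80% power at two-sided .05. The plan gives no r, and this case already lies within the 70% to 94% range. It does mean that the 12.7% increase should not be read as a demonstrated loss.

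Third, weighting and restricted randomization could produce a factor that is not a round number, such as 6.3, so the inference to .10 is conditional. That stands. The contradiction between the two sentences does not depend on it.

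Finally, the table has a footnote marker whose text is not visible, and the design figure is not shown. The marker is on the Q2c row only. Statements here about what is absent refer to the visible text.

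**Conclusion.** The point holds. Section 17.2 gives two significance levels for the same main-effect questions and does not reconcile them. The printed Q2a and Q2b MDEs fit the two-sided .10 (or one-sided .05) quantile to within .001, provided an unstated variance factor of 8 is accepted. Power at those MDEs under two-sided .05 runs from 70% to 94% as the factor goes from 8 to 4, so this does not show that the trial is underpowered. It shows that the stated 5% error, 80% power and MDEs have not been tied together.

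If factor 8 is right and two-sided .05 is the test level, the Q2b MDE is .516 / .547. That exceeds a medium effect if medium means 0.5, which is an assumption because the protocol gives no value. These figures rest on the normal approximation, no covariate adjustment and the derived N at 20% attrition. The matter should be settled before analysis because it fixes the decision threshold for two of the three main questions.

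**What to change.** 1. State one alpha, with its sidedness, for the tests of Q2a and Q2b. Two-sided .05 is the level that the first paragraph of 17.2 justifies.
2. Remove or reconcile the other sentence. If .10 was a planning value only, say so and give power at the test level. If .10 is the test level, correct the sentence that claims a 5% error.
3. State the formula and variance factor behind the Q2a and Q2b MDEs, including any covariate adjustment, and justify or correct the factor.
4. Say that Q2c is planned on a selection criterion, a correct-strategy probability of .95.
5. Print alpha in the table and recompute it to match. Without covariate adjustment, the two-sided .05 values are those in the last table of the working: the f = 8 row if that factor is justified, the f = 4 row if it is not.

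The cost is protocol wording and a recomputed table, with no extra families. The downside is that choosing two-sided .05 and keeping factor 8 makes the stated MDEs 12.7% larger, and the description of Q2b as powered for small to medium effects may then need to change.

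### The Q2a and Q2b minimum detectable effects do not follow from the stated sample sizes, 1:1 allocation and 80% power at either stated alpha

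*Combined protocol and SAP*

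**What the plan says.** Section 17.2 (Power Analysis) gives the ingredients of the calculation:

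- **Alpha and power.** The section first says "we chose a power convention of .80 with a two-sided alpha level of .05". Its next paragraph says "As recommended, we specified an alpha level of .10 and power of .80", without giving the sidedness of the .10.
- **Allocation.** At stage one: "The first stage randomization is allocated with a 1:1 ratio to group conditions". At stage two: "non-responders will also be randomized to second stage interventions with a 1:1 allocation".
- **Non-response.** "we estimate a potential 50% non-response rate for both the online and weekend condensed groups", which is the source of the 262 non-responders in the table (525 × 0.5 = 262.5).
- **Weighting.** "power needed to be estimated by addressing the restricted randomization scheme and appropriate weighting of the overrepresentation of responders", and a published SMART power procedure is cited. No numerical factor is given.

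The table, "ADAPT SMART Trial Minimally Detectable Effect (MDE) with .80 Power and 10% and 20% Attrition", has a column of total samples: 473 for Q2a and 236 for Q2b, each after 10% attrition. Q2a compares the two first-stage arms in full (A, B and C against D, E and F). Q2b compares the two second-stage options among non-responders (B and E against C and F). The printed effects at 10%/20% attrition are .324/.343 for Q2a and .458/.485 for Q2b. From the table the section concludes that the trial is "adequately powered to detect small to medium effects for Research Questions 2a, 2b, and 2c".

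**The concern.** With total N, equal allocation, alpha and power all stated, the detectable standardised difference between two groups is fixed unless some variance inflation is added. The four Q2a and Q2b cells are well above what these inputs give, by a constant proportion. Section 17.2 states no design effect, intraclass correlation or cluster size. Section 17.1 mentions non-independence only for the contrasts between embedded strategies, again without a factor.

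The table is the only numerical support in section 17.2 for the adequacy-of-power statement, and these are four of its six cells. As it stands, a reader cannot tell whether they contain a deliberate allowance, for instance for families attending the same workshop or booster group, or a slip in the sample size. The two readings differ in substance: if it is a slip, the table contains no clustering allowance at all.

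**Working it through.** **Inputs (section 17.2).** Power .80; alpha .05 two-sided, or .10 with sidedness unstated; 1:1 allocation at both stages. Totals at 10% attrition are printed: 473 and 236. Totals at 20% are derived the same way: 525 × 0.8 = 420 and 262 × 0.8 = 209.6, taken as 210.

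**Formula.** For two equal groups of independent families with SD 1:

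MDE = (z_α + z_.80) × √(4/N), with z_.80 = 0.8416.

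The values of z_α are 1.6449 (two-sided .10), 1.9600 (two-sided .05) and 1.2816 (one-sided .10). Example for Q2a at 10% attrition, two-sided .10: 2 × (1.6449 + 0.8416)/√473 = 4.973/21.749 = .2287.

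**Attempt to reproduce the table**

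| | Q2a 10% | Q2a 20% | Q2b 10% | Q2b 20% |
|---|---|---|---|---|
| Total N | 473 | 420 | 236 | 210 |
| Printed | .324 | .343 | .458 | .485 |
| Two-sided .10 | .2287 | .2427 | .3237 | .3432 |
| Two-sided .05 | .2576 | .2734 | .3647 | .3867 |
| One-sided .10 | .1952 | .2072 | .2764 | .2930 |

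No row reproduces the printed values. Using the noncentral t distribution moves the computed values by less than .002. Raising power to .90 or .95 does not reproduce the set either: for Q2a at 10% it gives .298 or .332 at two-sided .05, and .269 or .303 at two-sided .10.

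**Size of the gap**

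| | Q2a 10% | Q2a 20% | Q2b 10% | Q2b 20% |
|---|---|---|---|---|
| Variance ratio (printed/MDE)², two-sided .10 | 2.008 | 1.998 | 2.002 | 1.997 |
| Variance ratio, two-sided .05 | 1.582 | 1.574 | 1.577 | 1.573 |
| Variance ratio, one-sided .10 | 2.754 | 2.740 | 2.745 | 2.740 |
| Power at printed effect, two-sided .10 | .970 | .969 | .969 | .969 |
| Power at printed effect, two-sided .05 | .941 | .940 | .940 | .940 |
| Power at printed effect, one-sided .10 | .988 | .987 | .987 | .987 |

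Power is Φ(δ√N/2 − z_α). For Q2a at 10%, two-sided .10: Φ(.324 × 21.749/2 − 1.6449) = Φ(1.878) = .970.

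**What would produce the printed values.** Solving for N, N = 4(z_α + z_.80)²/δ², gives totals of 235.6, 210.2, 117.9 and 105.1 at two-sided .10. Each is about half the stated total. Putting half of each N into the formula gives .3234, .3432, .4578 and .4853, matching all four cells to within .001. Half N does not match at two-sided .05 (.3643, .3867, .5158, .5468) or one-sided .10 (.2761, .2930, .3909, .4144). The printed Q2a pair is also what the Q2b totals of 236 and 210 give at two-sided .10. The pattern fits per-arm n entered as total N, one halving too many, or a variance inflation of 2.

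**Could weighting explain it?** Q2a pools whole randomised arms and Q2b uses only non-responders randomised 1:1, so neither contrast needs unequal weights. Suppose they were applied anyway. With 1:1 randomisation at each stage, responders get weight 2 and non-responders weight 4. With 50% non-response and equal variances, the inflation for a pooled arm is the mean squared weight over the squared mean weight: ((4 + 16)/2)/3² = 10/9. For a single embedded strategy relative to its full arm it is 1.5, since n/2 families have weight 2 and n/4 have weight 4, giving 6n/(2n)² = 1.5/n. Applied to Q2a at 10%, these give .241 and .280 at two-sided .10, and .272 and .316 at two-sided .05. None is .324.

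**The case against.** The strongest objection is that this tests the table against a formula the plan does not say it used. Section 17.2 refers to a cited SMART procedure and to weighting for all three questions. That source, Figure 6 and the text of the table's footnote were not available for this check. So it cannot be said what the authors actually computed, and the cause stays open. It remains true that the printed values do not follow from the inputs the plan states. The footnote mark is on the Q2c row, which is not questioned here, and Figure 6 is cited for the allocation, which the text also gives. The analysis of covariance planned in section 17.1 would lower a detectable effect, not raise it.

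A second objection is that independent-family values could make the table worse. Section 5.2 describes workshops and booster groups attended by several families, so independence is doubtful in those conditions, and the larger printed values may be nearer the truth. This has force: the smaller values should not be printed without a plain statement of what they assume. It does not justify an unstated factor. The online programme and the individual booster are not delivered in groups, so the same inflation of 2 in both rows would itself need explaining.

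Third, the consequence is modest, because the discrepancy is in the safe direction relative to independence and no design decision turns on it. That is accepted. The conflict between the two alphas is a separate matter; the mismatch here is present at each of them.

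**Conclusion.** The point holds. The four Q2a and Q2b cells cannot be reproduced from the table's totals, 1:1 allocation and .80 power at two-sided .05, two-sided .10 or one-sided .10. Relative to independent families the printed effects are too large by a factor of 1.413 to 1.417 at two-sided .10, 1.254 to 1.258 at two-sided .05, and 1.655 to 1.659 at one-sided .10. At those effects the stated samples give about 97%, 94% and 99% power respectively.

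The calculation assumes independent families, equal groups, unit SD and no covariate adjustment. Treating the .10 as two-sided is an assumption. The match to half the stated N at that level describes a pattern and does not prove an error of a particular kind. The finding is one of non-reproducibility. It is not evidence that the trial is underpowered, and it does not overturn the small-to-medium conclusion.

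**What to change.** In section 17.2, settle on one alpha and its sidedness, state the formula behind the Q2a and Q2b rows, and say whether any variance inflation was intended.

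- **If inflation was intended**, for example for clustering in workshops or booster groups, give the factor with its ICC and cluster size, and compute the cells from it.
- **If none was intended**, replace the four cells. At two-sided .10 they become Q2a .229/.243 and Q2b .324/.343; at two-sided .05, Q2a .258/.273 and Q2b .365/.387. State beside the table that these assume independent families and no covariate adjustment.

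The cost is one or two sentences of assumptions and at most four recalculated cells. Enrolment and conduct are unaffected.
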